## 1.0 Background (Limit 1,000 words):

**Provide the scientific or scholarly background for the proposed Human Research. Discuss relevant prior experience or preliminary data (e.g., existing literature).**

Arthritis is one of the leading causes of pain, impairments of activities in daily life, and disability in people aged 45 and above. Of the 53 million adults diagnosed with arthritis, more than 22 million (42%) reported trouble with their activities of daily living due to arthritis. Osteoarthritis (OA) is the most common of the arthritic conditions, with the knee being the most commonly affected joint. Patients with chronic pain, such as knee OA pain, do not have sufficient pain relief, and this leads to decreased physical functioning and mobility disability. OA pain is characterized by altered pain and sensory processing in the central nervous system similar to other chronic pain syndromes. Because pharmacologic treatments can increase adverse events among older adults, there is a growing interest in non-pharmacological interventions targeting central nervous system pain processing for this population. Specifically, noninvasive brain stimulation, such as Transcranial Direct Current Stimulation (tDCS), has received significant attention for the treatment of pain in chronic conditions due to its neuromodulatory effect. tDCS involves the application of weak direct electric current to the head in a noninvasive and painless manner, leading to the modulation of the resting membrane potentials of neurons and alteration of the endogenous excitability of the targeted cortical area. This stimulation is believed to mediate analgesic effects by modulating pain processing pathways. Also, mindfulness-based meditation (MBM) has been shown to improve pain-related brain function and alleviate pain in multiple chronic pain conditions. Since tDCS is a noninvasive and safe approach to facilitate neuroplasticity, it may enhance the brain's ability to adaptively reorganize in response to other clinical interventions, including mindfulness-based interventions. Therefore, we will examine the effect of tDCS paired with MBM in older adults with knee OA pain. Our hypothesis is that remotely supervised tDCS paired with MBM at home will decrease clinical pain and OA-related clinical symptoms, improve physiopsychological pain processing, and increase participant satisfaction with treatment.

# IRB Protocol for Human Subjects Research

## 2.0 Lay Summary:

**Provide a brief description of the proposed research using terms that someone who is not familiar with the science or discipline can understand.**

Knee osteoarthritis pain is one of the most common pain conditions among people over 45 and pharmacological interventions do not adequately address this common comorbid condition. The proposed study examines an evidence-based nonpharmacological intervention targeting pain-related brain function: self-administered, remotely supervised transcranial direct current stimulation at home combined with mindful-based meditation. This study has the potential to significantly improve the self-management of pain, decrease public health expenditures, and improve the quality of life for older adults.

## 3.0 Purpose:

**Describe the purpose, specific aims, objectives, questions to be answered, hypotheses, and/or primary and secondary study endpoints of this Human Research protocol.**

The purpose of this project is to assess the effect of the self-administered tDCS paired with MBM in 200 older adults with knee OA. The specific aims are the following: determine the effects of active tDCS paired with active MBM on clinical pain and OA-related clinical symptoms (specific aim 1); determine the effects of active tDCS paired with active MBM on physiopsychological pain processing (specific aim 2); determine the effects of active tDCS paired with active MBM on participant satisfaction with treatment (specific aim 3); evaluate the effect of MBM paired with tDCS on pain-related brain function (specific aim 4); and evaluate the relationship between pain-related brain function and pain catastrophizing behavior and OA-related clinical pain (specific aim 5). The central hypothesis is that remotely supervised tDCS paired with MBM at home will decrease clinical pain and OA-related clinical symptoms, improve physiopsychological pain processing, increase participant satisfaction with treatment, and decrease maladaptive changes in pain-related brain function. The study endpoint is 4 months, including monthly follow-up telephone assessments for 3 months after the completion of intervention.

## 4.0 Funding Information:

**Indicate all sources of funding for the project, including gift funds, departmental funds, or other internal funding. For each funder, list the name of the funder, and the institutional proposal number or award number you received from Sponsored Projects. eIRB tip: For externally funded projects, the institutional proposal or award number provided must be linked in the “Study Funding Sources” section in eIRB.**

 No Funding	
	Name of funding source: National Institute of Health (NIH)

# IRB Protocol for Human Subjects Research

 Federal Funding , including flow-through federal funding (i.e., NIH, NSF, DoD, etc.)	Institutional Proposal or Award Number: 5R01NR019051-04
	eDoc # (for multi-site projects): NCT04375072
 Industry Funding	Name of funding source:
	Institutional Proposal or Award Number:
	eDoc #:
 Foundation Funding	Name of funding source:
	Institutional Proposal or Award Number:
 Department Funding	Name of funding source:
 Gift Funding	Name of funding source:
 Other	Name of funding source:

## 5.0 Resources Available to Conduct the Human Research:

**Describe the resources (facilities, time, emergency resources, etc.) available to recruit, consent, conduct study procedures, and analyze data.**

This study, funded by NIH, was approved by the IRB at the University of Texas Health Science Center at Houston and the IRB at the Florida State University at Tallahassee. On this R01 project, all the data will be collected at [name] laboratory in the UA College of Nursing building at a single site and continued from where the study has left off. Previous participant data will be compiled from the other previous sites and be used in UA. Adequate equipment and resources are available in the [name] laboratory to carry out the procedures and accommodate the personnel described in this proposal.

### Processing and Analysis of Imaging Data

Processing and analysis software will be used to analyze the image data collected within this project. This software will not be used for any of the medical purposes listed in the International Medical Device Regulators Forum, *Software as a Medical Device (SaMD): Key Definitions* document. In other words, the software will not be used for the purpose of:

- diagnosis, prevention, monitoring, treatment or alleviation of disease,
- diagnosis, monitoring, treatment, alleviation of or compensation for an injury,
- investigation, replacement, modification, or support of the anatomy or of a physiological process,
- supporting or sustaining life,
- control of conception,

# IRB Protocol for Human Subjects Research

- disinfection of medical devices,
- provide information by means of in vitro examination of specimens derived from the human body.
- provide means and suggestions for mitigation of a disease,
- provide information for determining compatibility, detecting, diagnosing, monitoring or treating physiological conditions, states of health, illnesses or congenital deformities,
- be an aid to diagnosis, screening, monitoring, determination of predisposition; prognosis, prediction, determination of physiological status.

Additionally, all software used to process and analyze image data collected during this project is used in “Exempted investigations” based on the Code of Federal Regulations Title 21 Section 812.2 (c)(3)(iv). In other words, the software

- is not used as a diagnostic procedure without confirmation of the diagnosis by another, medically established diagnostic product or procedure.

A Medical Device appendix will be submitted for any software used in this project that does not satisfy the above requirements.

## 6.0 Study Population:

### 6.1 Select all the categories of participants included in the research:

 Healthy adults	 Non-English-speaking subjects
 Non-healthy adults	 UA staff/faculty
 Children (under 18 years old) *	 UA students
 Pregnant women, neonates, and/or fetuses*	 Banner employees
 Prisoners*	 Refugees
 Native Americans, Alaskan Native, and Indigenous Populations*	 Other – please explain: Click or tap here to enter text.
 Adults unable to consent (i.e., cognitively impaired adults) *	

### 6.2 For each of the above selected categories, describe the inclusion and exclusion criteria. Indicate age range, gender, and ethnicity.

Similar to our previous work, participants who are 50-85 years old will be considered eligible if they (1) have symptomatic knee OA based on American College of Rheumatology clinical criteria, (2) have had knee OA pain in the past 3 months with an average of at least 30 on a 0-100 NRS for pain, (3) can speak and read English, and (4)

# IRB Protocol for Human Subjects Research

have no plan to change medication regimens for pain throughout the trial. The age range was selected to include a higher proportion of persons with knee OA pain. There will be no restrictions on gender or ethnicity. According to American College of Rheumatology criteria, participants should meet at least 3 of 6 criteria, including age > 50 years, experience stiffness, the physical property of being inflexible and hard to bend, < 30 minutes in a day, crepitus, bony tenderness, bony enlargement, and no palpable warmth. Participants will be excluded if they have any concurrent medical conditions that could confound the interpretation of outcome measures, pose a safety risk for any of the assessments or interventions, or preclude the successful completion of the protocol. Specific exclusion criteria are: (1) history of brain surgery, brain tumor, seizure, stroke, epilepsy, or intracranial metal implantation, (2) systemic rheumatic disorders, including rheumatoid arthritis, systemic lupus erythematosus, and fibromyalgia, (3) alcohol/substance abuse, (4) diminished cognitive function that would interfere with understanding study procedures (i.e., Mini-Mental Status Exam score  $\leq$  23), (5) prosthetic knee replacement or non-arthroscopic surgery to the affected knee, (6) hospitalization within the preceding year for psychiatric illness, (7) no access to a device (e.g., smartphone, computer) that can be used for secure video conferencing for real-time remote supervision, and (8) skin or scalp conditions that may be aggravated by tDCS stimulation.

Specific inclusion/exclusion criteria for Magnetic Resonance Imaging (MRI) procedures.

- Participants must be able to tolerate small, enclosed spaces and have no medical devices or implants on or in their bodies.
- On a case-by-case basis, and only if the provenance and safety of the implant can be established, individuals with certain implants may be able to undergo an MRI scan. Such implants may include, cardiac stents, carotid stents, cardiac valve replacements, bone and joint pins and screws, some IUD and birth control implants.
- Participants will be excluded from this study if they have any history of pacemakers or pacer wires, open heart surgery, artificial heart valves, aneurysm clips, cochlear implants, braces or extensive dental work, implanted electrical or mechanical devices, tissue expanders, foreign metallic objects from explosives, shrapnel or metalwork fragments, or artificial limbs. Participants will also be excluded if they are pregnant, claustrophobic, have tremors or cannot lie still for 1-2 hours, or weight more than 300 pounds.

**6.3 Describe the total number of subjects to be enrolled locally under this IRB approval. If obtaining specimens, specify the maximum number of specimens needed for this project.**

# IRB Protocol for Human Subjects Research

The number of subjects who are expected to be enrolled and screened is 240, and the number of subjects needed to complete the research procedures (i.e., numbers of subjects excluding screen failures.) is 200. The number of subjects who are expected to be enrolled and screened for MRI is 80, and the number of subjects needed to complete the MRI procedures is 40. Locally, we will recruit 36 participants in UA. 28 participants will be for both the tDCS/MBM and MRI procedures combined and 8 participants will be for the tDCS/MBM procedure alone.

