## 9.0 Consenting Process:

**9.1 Indicate the informed consent process(es) and/or document(s) for the study. Check all that apply.**

# IRB Protocol for Human Subjects Research

Written Consent
 Informed Consent (ICF) – written or electronically signed form
 Parental Permission – written or electronically signed form
 Assent (participants under 18) – written or electronically signed form
 Combined ICF/PHI Authorization – written or electronically signed form
 Protected Health Information (PHI) Authorization – written or electronically signed
 Translated Consent/Assent – written or electronically signed form(s)
 Short Consent Form – written or electronically signed form (see guidance on Short Form process )
 Debriefing Script or Form – document used to properly inform subjects of the study's purpose when intentionally deceived

  

Oral/Online/Unsigned Consent
 Informed Consent – oral script/online/unsigned
 Parental Permission – oral script/online/unsigned
 Assent – oral script/online/unsigned
 Translated Consent/Assent – oral script/online/unsigned

  

Waivers of Informed Consent and/or PHI Authorization
 Waiver of Consent
 Full Waiver of PHI Authorization
 Partial Waiver of PHI for Screening Purposes

**9.2 Describe in detail the consent processes checked above, including any waiting period for subjects to sign the consent, steps to minimize the possibility of coercion or undue influence, and the language used by those obtaining consent.**

Subjects will have the option to participate in either the tDCS/MBM portion of the study alone or combined with the MRI scan portion at the start of the recruitment process. If the subject decides to participate in tDCS/MBM, an informed consent form will be given. There will be additional check box for the subject who decides to participate in MRI scan and additional signature will be collected.

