Subjects will participate in the study only after they provide signed consent. Participation in this study is completely voluntary. All participants will be informed of the nature of the procedures and associated risks.

The consented subject will be screened for any contraindications to MRI and magnetic materials. The investigator or MRI Technologist will explain the MRI system and the scan that the subject will take part in. The subject will be asked to lie down on the scanner bed. Some part of the subjects' body may be covered or enclosed within an FDA or UA

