# IRB Protocol for Human Subjects Research

## 10.2 Description of research procedures.

Participants who meet eligibility criteria and give informed consent will be randomly assigned at a ratio of 1:1:1:1 to one of the four groups: (a) active tDCS paired with active MBM (n=50), (b) sham tDCS paired with active MBM (n=50), (c) active tDCS paired with sham MBM (n=50), or (d) sham tDCS paired with sham MBM (n=50) using the order of entrance in the study and previous randomization list generated via SAS software. The randomization will balance the allocation of patients to the study arms with respect to distributions of age, race, and sex. tDCS with a constant current intensity of 2 mA will be applied for 20 minutes per session daily for 2 weeks (Monday to Friday) via the Soterix 1x1 tDCS mini-CT Stimulator device (Soterix Medical Inc., NY; 6.5 inches long, 3 inches wide, 0.7 inches thick) with headgear and 5x7 cm pre-saturated, single use, individually packed sponge electrodes. The FDA has ruled that the aforementioned tDCS stimulator is a “non-significant risk” device, a requirement for Investigational Device Exceptions. The sponge electrodes snap into the custom headgear, which is secured to the participant’s head for simple and fail-safe electrode preparation. This single-position headgear with clearly labeled sponge markers eliminates room for user error and helps conserve accurate and reproducible sponge placement. Participants can only administer a stimulation session via the Soterix 1x1 tDCS mini-CT Stimulator device after being provided a single-use unlock code by the research staff once proper contact quality is achieved (only the on/off button will be adjustable by the study participants; they will not be able to adjust the device settings). After the participant enters the unlock code, the screen on the device will show a timer that counts down the minutes until the end of the session. At 20 minutes, the device will turn off automatically, and study staff will instruct the participant to remove the headset and discard the sponges and to safely store all materials for the next session. For sham stimulation, the electrodes will be placed in the same positions as for active stimulation, but the stimulator will only deliver 2 mA current for 30 seconds. This sham stimulation method has been shown to be reliable and indistinguishable from active treatment. During each tDCS session, participants will practice MBM. The meditation intervention will be applied simultaneously with tDCS for 20 minutes per session daily for 2 weeks by a recorded meditation on a CD. Participants will be provided with a CD player and earphones. The recording will instruct participants to close their eyes, connect to the openness of one’s mind, and mindfully maintain and deepen the connection through breathing with more openness and awareness. The sham MBM intervention will be delivered via a CD player that will look identical in both active and sham MBM. The sham recording will instruct participants to relax and take deep breaths every 3 minutes without the specific mindfulness-based instructions (e.g., practicing mindful attention to the breath in a non-evaluative manner). All other aspects of the sham MBM intervention (e.g., body position, time spent listening to instructions, eyes closed) will match the active MBM.

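### Does a target of 40 MRI completers over four arms leave specific aim 4 too weak to be worth testing as planned?

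*Combined protocol and SAP*

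**What the plan says.** Section 6.3 gives two study-wide imaging counts. The target for completed scans reads: "and the number of subjects needed to complete the MRI procedures is 40". The count at the screening stage is twice as large: "The number of subjects who are expected to be enrolled and screened for MRI is 80". The section then gives the share of the current site (UA), 36 participants, of whom "28 participants will be for both the tDCS/MBM and MRI procedures combined" and 8 have no MRI. Section 5.0 describes a continuing study in which data from earlier sites are pooled with those from UA.

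Section 3.0 lists the imaging-related question as one of five aims: "evaluate the effect of MBM paired with tDCS on pain-related brain function (specific aim 4"). The central hypothesis there predicts that treatment will improve several outcomes "and decrease maladaptive changes in pain-related brain function". Section 11.1 repeats the hypothesis but names only aims 1 to 3 as the means of testing it.

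Section 10.2 randomises equally to four arms (tDCS active or sham, crossed with meditation active or sham), 50 per arm, by order of entry and an existing list. On balance it says: "The randomization will balance the allocation of patients to the study arms with respect to distributions of age, race, and sex". MRI participation is not among those factors. Section 9.2 lets participants choose the main study alone or "combined with the MRI scan portion at the start of the recruitment process". It adds: "The consented subject will be screened for any contraindications to MRI and magnetic materials".

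The schedule in section 10.2 has two MRI time points, near the baseline and last visits, and gives MRI no outcome label. It lists cortical response by fNIRS as a secondary outcome.

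**The concern.** Aim 4 asks about a treatment effect and the hypothesis gives its direction, so a reader expects a comparison between arms. Forty completers over four arms is 10 per arm at best, and no MRI measure, contrast or effect size is offered in support. If the analysis were active tDCS plus active meditation against double sham, a null result would say little. A significant result would tend to overstate the effect, because the observed difference would have to reach 0.94 SD.

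Two features seem to add to the weakness. MRI is the participant's choice, it can be known before allocation, and it is not balanced, so the 10 per arm could turn out uneven. And UA plans 28 MRI participants, which leaves at least 12 to come from elsewhere, with no count given.

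At stake would be an aim reported as tested when the data could support only a wide estimate. The primary outcome, pain on the NRS, is not affected.

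**Working it through.** **Inputs from the protocol.** 40 MRI completers, 80 screened and 28 at UA (6.3); four arms, 1:1:1:1, 50 per arm (10.2); two scans per participant (10.2). The 40 cannot be reproduced, because no inputs for it are given.

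**Assumptions, not in the documents.** Two-sided 5% level; true effect 0.8 SD, with 0.5 and 1.0 SD as a range; baseline-to-final correlation r of 0.5 to 0.7.

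**Step 1: arm sizes.** 40/4 = 10 per arm. Each main effect compares two arms with two: 20 v 20. UA alone: 28/4 = 7 per arm.

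**Step 2: pairwise contrast, 10 v 10, unadjusted.** Noncentrality = d / sqrt(2/n) = 0.8 / sqrt(0.2) = 1.79 on 18 df; critical t = 2.101. Power = 39.5% (18.5% at 0.5 SD, 56.2% at 1.0 SD). The smallest significant difference is 2.101 × sqrt(0.2) = 0.94 SD. The effect detectable with 80% power is 1.32 SD. At 7 per arm, power at 0.8 SD is 28.1%.

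**Step 3: the other readings that the design allows.** Adjusting for the baseline scan divides the effect by sqrt(1 − r²), which is 0.866 at r = 0.5 and 0.714 at r = 0.7. Power at 0.8 SD:

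| Contrast | Unadjusted | r = 0.5 | r = 0.7 |
|---|---|---|---|
| One arm v one arm, 10 v 10 | 39.5% | 50% | 66% |
| Main effect, 20 v 20 | 69% | 81% | 93% |

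If aim 4 rests on fNIRS, the planned arms are 50 and an unadjusted pairwise contrast has about 98% power at 0.8 SD.

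**Step 4: what balancing on MRI opt-in would gain.** If 40 completers fall at random over 4 × 50, some arm has 7 or fewer in about 56% of allocations. That is the chance for any of four arms; for the two arms of one contrast it is about 30%. Uneven splits cost little. Even 7 v 13 has 36.5% power against 39.5% for 10 v 10. Averaged over all random splits, power is about 38%. For 28 of 36 UA participants (assuming 9 per arm), it is about 27.7% against 28.1% for 7 v 7. The gain is roughly 1.5 percentage points in the first case and half a point in the second.

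**Step 5: 28 against 40.** 40 − 28 = 12. One figure is a local share and the other a study-wide total, so they do not conflict.

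**The case for a change.** The strongest case for acting is that no reading makes aim 4 comfortable without help. The unadjusted main effect has 69%, below the usual 80%. It also answers a different question: what tDCS or meditation each adds, where the aim speaks of the pair. The combined effect keeps the 10 v 10 precision. A pairwise comparison at 80% power for 0.8 SD would need 26 per arm, or 104 completers. If aim 4 is not about MRI, two scans per participant serve no aim named as theirs. The remedy looks cheap: name the measure and contrast, call the aim exploratory, and balance the remaining UA participants on opt-in.

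The arithmetic in this stands, and so does the observation that the protocol is silent on the MRI measure and contrast. It does not show an error in the plan. The low figure depends on choosing the pairwise contrast, ignoring the baseline scan and assuming 0.8 SD. The protocol makes none of these choices and plans no MRI test or efficacy claim. It is equally silent on power for every other outcome, so the silence is not peculiar to imaging.

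The balancing proposal is the only part that would alter conduct, and it does not hold up. If opt-in precedes allocation, chance imbalance in it does not bias the comparison. Replacing the rest of an existing list mid-trial assumes that earlier sites left the arms level, which no section says. If they did not, a fresh equal list could work against the planned 50 per arm.

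**Conclusion.** No change is called for. An optional imaging component of 40 is a fair trade-off between cost and precision in a trial whose primary outcome is pain. What is unwritten (the MRI measure, the contrast, the use of the baseline scan) can be settled sensibly before analysis. A competent analyst would fit a baseline-adjusted model, report estimates with 95% intervals, and treat the imaging results as exploratory.

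The size of the issue depends on choices left open. At 0.8 SD and a two-sided 5% level, power runs from 39.5% (pairwise, unadjusted) to about 93% (main effect, r = 0.7), and is about 98% if fNIRS carries the aim. The effect size, test level and correlations are assumptions. If the true effect were 0.5 SD, the unadjusted pairwise figure would be 18.5% and the main effect about 34%; a null MRI result should then be read only as a wide interval. Balancing on opt-in would add about 1.5 percentage points at most and is not worth disturbing the randomisation list.
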